##### 4.5.2 Echocardiogram

The primary ECHO objective is to evaluate the effect of ZX008 0.8 mg/kg/day (max 30 mg/day) on the mitral and aortic valves, and in particular evaluating for the development of VHD and PAH.

The number and percentage of subjects with each category of valvular regurgitation will be calculated by regimen and visit for each valve (Mitral, Aortic, Tricuspid, and Pulmonary), based on age (where appropriate).

PASP will be analyzed for mean, mean maximum change from baseline at each time point, as well as changes in PASP compared to baseline using 5, 10 and 15 mmHg differences. Abnormal values will be categorized by regimen and visit.

The primary analysis of the mitral and aortic valves is the change from baseline in regurgitation category between treatment and placebo and will be performed using an ANOVA model with effect for treatment.

#### 4.6 Secondary Analyses

Analyses conducted with 0.8 mg/kg/day (max 30 mg/day) ZX008 will be conducted with 0.2 mg/kg/day ZX008. Central tendency analyses will be conducted to include per-visit data and changes from baseline and placebo for the ECG and ECHO values for all subjects. The variables for analysis are listed in sections 2.3.1.2 and 2.3.2.2.

#### 4.7 Additional Analysis

Additional analysis may be used, as appropriate.

#### 4.8 Categorical Analysis

Categorical data will be reported as both numbers and percentages and will include changes from baseline in both ECG and ECHO variables.

Statistical Analysis Plan	
Status: Final Version 1.0	Revised: 09Jun2020

## 5. Tables, Figures, and Listings

Number	Title
Table 1.1.1	Means, Mean Differences from Baseline and Upper Bound of One-Sided 95% CI from ANOVA for ECG Data - QTcF, Safety Population - Males and Females, 0 to <12 Years
Table 1.1.2	Means, Mean Differences from Baseline and Upper Bound of One-Sided 95% CI from ANOVA for ECG Data - QTcF, Safety Population - Males, 12 to 18 Years
Table 1.1.3	Means, Mean Differences from Baseline and Upper Bound of One-Sided 95% CI from ANOVA for ECG Data - QTcF, Safety Population - Females, 12 to 18 Years
Table 1.1.4	Means, Mean Differences from Baseline and Upper Bound of One-Sided 95% CI from ANOVA for ECG Data - QTcF, Safety Population - Males, 0 to <12 Years
Table 1.1.5	Means, Mean Differences from Baseline and Upper Bound of One-Sided 95% CI from ANOVA for ECG Data - QTcF, Safety Population - Females, 0 to <12 Years
Table 1.2.1	Means, Mean Differences from Baseline and Upper Bound of One-Sided 95% CI from ANOVA for ECG Data - Heart Rate, Safety Population - Males and Females, 2 to < 6 Years
Table 1.2.2	Means, Mean Differences from Baseline and Upper Bound of One-Sided 95% CI from ANOVA for ECG Data - Heart Rate, Safety Population - Males and Females, 6 to < 12 Years
Table 1.2.3	Means, Mean Differences from Baseline and Upper Bound of One-Sided 95% CI from ANOVA for ECG Data - Heart Rate, Safety Population - Males and Females, 12 to 18 Years
Table 1.3.1	Means, Mean Differences from Baseline and Upper Bound of One-Sided 95% CI from ANOVA for ECG Data - QRS Duration, Safety Population - Males and Females, 2 to < 6 Years
Table 1.3.2	Means, Mean Differences from Baseline and Upper Bound of One-Sided 95% CI from ANOVA for ECG Data - QRS Duration, Safety Population - Males and Females, 6 to < 12 Years
Table 1.3.3	Means, Mean Differences from Baseline and Upper Bound of One-Sided 95% CI from ANOVA for ECG Data - QRS Duration, Safety Population - Males and Females, 12 to 17 Years
Table 1.3.4	Means, Mean Differences from Baseline and Upper Bound of One-Sided 95% CI from ANOVA for ECG Data - QRS Duration, Safety Population - Males and Females, 18 Years
Table 1.4.1	Means, Mean Differences from Baseline and Upper Bound of One-Sided 95% CI from ANOVA for ECG Data - PR-Interval, Safety Population - Males and Females, 2 to < 6 Years
Table 1.4.2	Means, Mean Differences from Baseline and Upper Bound of One-Sided 95% CI from ANOVA for ECG Data - PR-Interval, Safety Population - Males and Females, 6 to < 12 Years
Table 1.4.3	Means, Mean Differences from Baseline and Upper Bound of One-Sided 95% CI from ANOVA for ECG Data - PR-Interval, Safety Population - Males and Females, 12 to 17 Years
Table 1.4.4	Means, Mean Differences from Baseline and Upper Bound of One-Sided 95% CI from ANOVA for ECG Data - PR-Interval, Safety Population - Males and Females, 18 Years
Table 1.5	Means, Mean Differences from Baseline, and Mean Differences from Placebo and Baseline for ECG Data - QT-Interval, Safety Population
Table 2.1.1	Categorical Summary of ECG Data - QTcF, Safety Population - Males and Females, 0 to <12 Years
Table 2.1.2	Categorical Summary of ECG Data - QTcF, Safety Population - Males, 12 to 18 Years
Table 2.1.3	Categorical Summary of ECG Data - QTcF, Safety Population - Females, 12 to 18 Years
Table 2.1.4	Categorical Summary for ECG Data - QTcF Change from Baseline, Safety Population - Males and Females, 0 to <12 Years
Table 2.1.5	Categorical Summary for ECG Data - QTcF Change from Baseline, Safety Population - Males, 12 to 18 Years
Table 2.1.6	Categorical Summary for ECG Data - QTcF Change from Baseline, Safety Population - Females, 12 to 18 Years
Table 2.2.1	Categorical Summary of ECG Data - Heart Rate and Change from Baseline, Safety Population - Males and Females, 2 to <6 Years

Statistical Analysis Plan	
Status: Final Version 1.0	Revised: 09Jun2020

Number	Title
Table 2.2.2	Categorical Summary of ECG Data - Heart Rate and Change from Baseline, Safety Population - Males and Females, 6 to < 12 Years
Table 2.2.3	Categorical Summary of ECG Data - Heart Rate and Change from Baseline, Safety Population - Males and Females, 12 to 18 Years
Table 2.3.1	Categorical Summary of ECG Data - QRS Duration, Safety Population - Males and Females, 2 to < 6 Years
Table 2.3.2	Categorical Summary of ECG Data - QRS Duration, Safety Population - Males and Females, 6 to < 12 Years
Table 2.3.3	Categorical Summary of ECG Data - QRS Duration, Safety Population - Males and Females, 12 to 17 Years
Table 2.3.4	Categorical Summary of ECG Data - QRS Duration, Safety Population - Males and Females, 18 Years
Table 2.4.1	Categorical Summary of ECG Data - PR-Interval, Safety Population - Males and Females, 2 to < 6 Years
Table 2.4.2	Categorical Summary of ECG Data - PR-Interval, Safety Population - Males and Females, 6 to < 12 Years
Table 2.4.3	Categorical Summary of ECG Data - PR-Interval, Safety Population - Males and Females, 12 to 17 Years
Table 2.4.4	Categorical Summary of ECG Data - PR-Interval, Safety Population - Males and Females, 18 Years
Table 2.5.1	Results to Support Heat Maps of Mitral Valve Results, Safety Population
Table 2.5.2	Results to Support Heat Maps of Aortic Valve Results, Safety Population
Table 2.5.3	Results to Support Heat Maps of Tricuspid Valve Results, Safety Population
Table 2.5.4	Results to Support Heat Maps of Pulmonic Valve Results, Safety Population
Table 3	ECG Classification by Dosing and Visit, Safety Population
Table 4.1.1	Number of Subjects within Each Regurgitation Score by Visit - Mitral Valve, Safety Population
Table 4.1.2	Number of Subjects within Each Regurgitation Score by Visit - Aortic Valve, Safety Population
Table 4.1.3	Number of Subjects within Each Regurgitation Score by Visit - Tricuspid Valve, Safety Population
Table 4.1.4	Number of Subjects within Each Regurgitation Score by Visit - Pulmonic Valve, Safety Population
Table 4.2	Summary of Number of ECHOs per Subject, Safety Population
Table 5.1.1	Means, Mean Differences from Baseline at End of Study and Maximum and Upper Bound of One-Sided 95% CI from ANOVA for ECHO Data - PASP, Safety Population
Table 5.1.2	Means, Mean Differences from Baseline by Visit and Upper Bound of One-Sided 95% CI from ANOVA for ECHO Data - RVOT, Safety Population
Table 5.1.3	Means, Mean Differences from Baseline by Visit and Upper Bound of One-Sided 95% CI from ANOVA for ECHO Data - PVPR, Safety Population
Table 6.1.1	Number of Subjects with Mitral Valvular Heart Disease Per FDA Definitions, Safety Population
Table 6.1.2	Number of Subjects with Aortic Valvular Heart Disease Per FDA Definitions, Safety Population
Table 6.2.1	Number of Subjects with Any $\geq$ Trace Regurgitation Post-Baseline - Mitral Valve, Safety Population
Table 6.2.2	Number of Subjects with Any $\geq$ Trace Regurgitation Post-Baseline - Aortic Valve, Safety Population
Table 6.3.1	Number of Subjects with $\geq$ Trace Regurgitation at End of Study - Mitral Valve, Safety Population
Table 6.3.2	Number of Subjects with $\geq$ Trace Regurgitation at End of Study - Aortic Valve, Safety Population
Table 6.4	Number of Subjects with Clinically Confirmed Valvular Heart Disease (VHD), Safety Population

Statistical Analysis Plan	
Status: Final Version 1.0	Revised: 09Jun2020

Number	Title
Table 6.5.1	Number of Subjects with Normal or Trace at Baseline and Any $\geq$ Mild at End of Study - Tricuspid Valve, Safety Population
Table 6.5.2	Number of Subjects with Normal or Trace at Baseline and Any $\geq$ Mild at End of Study - Pulmonic Valve, Safety Population
Table 6.6	Number of Subjects with Any PASP Change from Baseline $>10$ , $>15$ , $>20$ mmHg, Safety Population
Table 6.7	Number of Subjects with Any PASP $>35$ mmHg, Safety Population
Table 6.8	Number of Subjects with RVOT $\geq 100$ msec at Baseline and $<100$ msec at EOS/ET, Safety Population
Table 6.9	Number of Subjects with Any RVOT $<100$ msec Post-Baseline, Safety Population
Table 7	Categorical Summary of ECHO Data, Difference from Baseline, Safety Population
Table 8	ECG Overall Findings by Dosing, Visit, and Abnormal Comment, Safety Population
Figure 1.1	Plot of Mean (SE) QTcF by Visit, Safety Population - Males and Females, 0 to $<12$ Years
Figure 1.2	Plot of Mean (SE) QTcF by Visit, Safety Population - Males, 12 to 18 Years
Figure 1.3	Plot of Mean (SE) QTcF by Visit, Safety Population - Females, 12 to 18 Years
Figure 2.1	Plot of Mean (SE) Heart Rate by Visit, Safety Population - Males and Females, 2 to $<6$ Years
Figure 2.2	Plot of Mean (SE) Heart Rate by Visit, Safety Population - Males and Females, 6 to $<12$ Years
Figure 2.3	Plot of Mean (SE) Heart Rate by Visit, Safety Population - Males and Females, 12 to 18 Years
Figure 3.1	Plot of Mean (SE) QRS Duration by Visit, Safety Population - Males and Females, 2 to $<6$ Years
Figure 3.2	Plot of Mean (SE) QRS Duration by Visit, Safety Population - Males and Females, 6 to $<12$ Years
Figure 3.3	Plot of Mean (SE) QRS Duration by Visit, Safety Population - Males and Females, 12 to 17 Years
Figure 3.4	Plot of Mean (SE) QRS Duration by Visit, Safety Population - Males and Females, 18 Years
Figure 4.1	Plot of Mean (SE) PR Interval by Visit, Safety Population - Males and Females, 2 to $<6$ Years
Figure 4.2	Plot of Mean (SE) PR Interval by Visit, Safety Population - Males and Females, 6 to $<12$ Years
Figure 4.3	Plot of Mean (SE) PR Interval by Visit, Safety Population - Males and Females, 12 to 17 Years
Figure 4.4	Plot of Mean (SE) PR Interval by Visit, Safety Population - Males and Females, 18 Years
Figure 5.1	Plot of Mean (SE) QTcF Change from Baseline by Visit, Safety Population - Males and Females, 0 to $<12$ Years
Figure 5.2	Plot of Mean (SE) QTcF Change from Baseline by Visit, Safety Population - Males, 12 to 18 Years
Figure 5.3	Plot of Mean (SE) QTcF Change from Baseline by Visit, Safety Population - Females, 12 to 18 Years
Figure 6.1	Plot of Mean (SE) Heart Rate Change from Baseline by Visit, Safety Population - Males and Females, 2 to $<6$ Years
Figure 6.2	Plot of Mean (SE) Heart Rate Change from Baseline by Visit, Safety Population - Males and Females, 6 to $<12$ Years
Figure 6.3	Plot of Mean (SE) Heart Rate Change from Baseline by Visit, Safety Population - Males and Females, 12 to 18 Years
Figure 7.1	Plot of Mean (SE) QRS Change from Baseline by Visit, Safety Population - Males and Females, 2 to $<6$ Years
Figure 7.2	Plot of Mean (SE) QRS Change from Baseline by Visit, Safety Population - Males and Females, 6 to $<12$ Years
Figure 7.3	Plot of Mean (SE) QRS Change from Baseline by Visit, Safety Population - Males and Females, 12 to 17 Years

Statistical Analysis Plan	
Status: Final Version 1.0	Revised: 09Jun2020

Number	Title
Figure 7.4	Plot of Mean (SE) QRS Change from Baseline by Visit, Safety Population - Males and Females, 18 Years
Figure 8.1	Plot of Mean (SE) PR-Interval Change from Baseline by Visit, Safety Population - Males and Females, 2 to < 6 Years
Figure 8.2	Plot of Mean (SE) PR-Interval Change from Baseline by Visit, Safety Population - Males and Females, 6 to < 12 Years
Figure 8.3	Plot of Mean (SE) PR-Interval Change from Baseline by Visit, Safety Population - Males and Females, 12 to 17 Years
Figure 8.4	Plot of Mean (SE) PR-Interval Change from Baseline by Visit, Safety Population - Males and Females, 18 Years
Figure 9.1	Change in Category Between Baseline (Visit 1) and Visit 8 - Mitral Valve, Safety Population
Figure 9.2	Change in Category Between Baseline (Visit 1) and Visit 8 - Aortic Valve, Safety Population
Figure 9.3	Change in Category Between Baseline (Visit 1) and Visit 8 - Tricuspid Valve, Safety Population
Figure 9.4	Change in Category Between Baseline (Visit 1) and Visit 8 - Pulmonic Valve, Safety Population
Figure 9.5	Change in Category Between Baseline (Visit 1) and Visit 12 - Mitral Valve, Safety Population
Figure 9.6	Change in Category Between Baseline (Visit 1) and Visit 12 - Aortic Valve, Safety Population
Figure 9.7	Change in Category Between Baseline (Visit 1) and Visit 12 - Tricuspid Valve, Safety Population
Figure 9.8	Change in Category Between Baseline (Visit 1) and Visit 12 - Pulmonic Valve, Safety Population
Figure 9.9	Change in Category Between Visit 8 and Visit 12 - Mitral Valve, Safety Population
Figure 9.10	Change in Category Between Visit 8 and Visit 12 - Aortic Valve, Safety Population
Figure 9.11	Change in Category Between Visit 8 and Visit 12 - Tricuspid Valve, Safety Population
Figure 9.12	Change in Category Between Visit 8 and Visit 12 - Pulmonic Valve, Safety Population
Figure 10	Mean Pulmonary Artery Systolic Pressure by Visit, Safety Population
Figure 11	Mean Right Ventricular Outflow Tract Acceleration Time by Visit, Safety Population
Figure 12	Mean Pulmonic Valve Peak Regurgitation Jet Velocity by Visit, Safety Population
Figure 13	Scatter Plot of Pulmonary Artery Systolic Pressure by Visit, Safety Population
Listing 1.1	Raw ECG Data by Subject and Visit, Safety Population
Listing 1.2	ECG Comments, Safety Population
Listing 2.1	Raw Echo Data by Subject and Visit, Safety Population

Statistical Analysis Plan	
Status: Final Version 1.0	Revised: 09Jun2020

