#### 2.3.1.2 Other ECG Analyses

Other secondary endpoints that will be presented by dose and subgroups are:

- Mean QTcF duration including changes from baseline ( $\Delta\text{QTcF}$ )
- Mean QRS duration (including changes from baseline ( $\Delta\text{QRS}$ ) and from placebo and baseline ( $\Delta\Delta\text{QRS}$ ))
- Mean PR interval measurements (including changes from baseline ( $\Delta\text{PR}$ ) and from placebo and baseline ( $\Delta\Delta\text{PR}$ ))
- Mean Heart rate (including changes from baseline ( $\Delta\text{HR}$ ) and from placebo and baseline ( $\Delta\Delta\text{HR}$ ))
- Categorical analyses for each variable and subgroup listed below:
  - QTcF (number and percentage of subjects, by dose)

Age	Gender	Values
0 to < 12 years	Males and Females	< 320 ms
		$\geq 320\text{ms to } \leq 450\text{ ms}$
		> 450 ms to $\leq 480\text{ ms}$
		> 480 ms
12 to 18 years	Males	< 320 ms
		$\geq 320\text{ ms to } \leq 450\text{ ms}$
		> 450 ms to 500 ms
		> 500 ms
12 to 18 years	Females	< 320 ms
		$\geq 320\text{ ms to } \leq 470\text{ ms}$
		> 470 ms to $\leq 500\text{ ms}$
		> 500 ms

Statistical Analysis Plan	
Status: Final Version 1.0	Revised: 09Jun2020

- For all ages QTcF changes from baseline (number and percentage of subjects, by dose)
  - ≤ 30 ms
  - > 30 ms to ≤ 60 ms
  - > 60 ms
- QRS (number and percentage of subjects, by dose)

Age	Gender	Values
2 to <6 years	Males and Females	≤ 90 ms
		>90ms to ≤100ms
		> 100 ms
		≤ 100 ms
6 to < 12 years	Males and Females	> 100 ms to ≤ 110 ms
		> 110 ms
		≤110ms
		>110 ms to ≤ 120ms
12 to 18 years	Males and Females	>120ms
		≤ 90 ms

- PR (number and percentage of subjects, by dose)

Age	Gender	Values
2 to <6 years	Males and Females	≤ 90 ms
		> 90ms to ≤ 150 ms
		>150 ms
6 to < 12 years	Males and Females	≤ 100 ms
		> 100 ms to ≤ 170 ms
		>170 ms
12 to 17 years	Males and Females	≤110ms
		>110 ms to ≤ 180ms
		>180ms
18 years	Males and Females	≤120 ms
		>120 ms to ≤ 220ms
		>220 ms

- Heart rate (number and percentage of subjects, by dose)

Age	Gender	Values
2 to <6 years	Males and Females	<80 bpm
		≥80 bpm to ≤140bpm
		> 140 bpm to ≤ 180 bpm
		> 180 bpm Increase or decrease from baseline > 20 bpm
6 to < 12 years	Males and Females	<60 bpm
		≥60 bpm to ≤120bpm
		> 120 bpm to ≤ 150 bpm
		> 150 bpm Increase or decrease from baseline > 20 bpm
12 to 18 years	Males and Females	< 50 bpm
		≥50 bpm to ≤100bpm
		> 100 bpm to ≤ 150 bpm

Statistical Analysis Plan

Status: Final Version 1.0

Revised: 09Jun2020

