#### 2.3.2.2 Other Echocardiographic Analysis

Other, secondary endpoints include:

- Number of subjects within each tricuspid or pulmonic regurgitation score by visit
- Number of subjects with normal or trace tricuspid or pulmonic regurgitation at baseline and  $\geq$  mild tricuspid or pulmonic regurgitation at end of study
- Pulmonary Artery Systolic Pressure (PASP)
  - Mean change from baseline at end of study
  - Mean maximum change from baseline at anytime during therapy
  - Number of subjects with change from baseline at anytime during therapy:
    - > 10 mmHg

Statistical Analysis Plan	
Status: Final Version 1.0	Revised: 09Jun2020

- >15 mmHg
- >20 mmHg
  - Number of subjects with PASP>35 mmHg at anytime during therapy
- Right ventricular outflow tract (RVOT) acceleration time (will be used only as confirmatory variables for pulmonary hypertension)
  - Mean Change from Baseline in RVOT (msec) by visit
  - Number of subjects with Baseline  $\geq$ 100 msec and at EOS/ET RVOT <100 msec
  - Number of subjects with any RVOT measurement < 100 msec post-baseline

Summary of the number of ECHOs per subject will also be presented.

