### 3.2.7 Alert Criteria

Echocardiographic alert criteria included:

- Valve regurgitation (aortic or mitral)
- $\geq$  moderate valve regurgitation (tricuspid or pulmonic)
- Mean mitral valve gradient  $\geq$  4 mmHg
- Mean aortic valve gradient  $\geq$  15 mmHg
- Mean tricuspid valve gradient  $\geq$  4 mmHg
- Peak pulmonic valve gradient  $\geq$  21 mmHg
- Tricuspid regurgitation jet velocity > 2.8 meters/sec with or without the findings OR
- One of the following findings in the absence of being able to measure tricuspid regurgitation jet velocity:
  - Change in right ventricle/left ventricle basal diameter ratio > 1.0
  - Right ventricular outflow tract flow acceleration time < 100 msec
  - Dilatation of the inferior cava vein (diameter > 21mm and <50% inspiratory collapse) and/or right atrial dilatation
  - Change in the geometry of the interventricular septum in systole (flattening) with left ventricular eccentricity index >1.1 in systole and/or in diastole
  - Early diastolic pulmonary regurgitation velocity >2.2 m/sec
  - Tricuspid Annular Plane Systolic Excursion below 18 mm or below Z-score – 2

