#### 4.5 Primary Analyses

##### 4.5.1 Electrocardiogram

The primary ECG objective is to evaluate the effect of ZX008 0.8 mg/kg/day (max 30 mg/day) on QTcF.

The primary analysis of the QTcF is the mean baseline-adjusted difference between treatment and placebo and will be performed using an analysis of variance (ANOVA) for each post-dose time point. The ANOVA model will include a fixed effect for treatment. The upper bound of the one-sided 95% CI (or, equivalently, two-sided 90% CI) of the mean baseline-adjusted difference between treatment and placebo QTcF ( $\Delta\Delta\text{QTcF}$ ) will be calculated from the ANOVA for each time point.

The general formula to calculate the  $\Delta\Delta\text{QTcF}$  at the  $i$ th timepoint is:

Mean  $\Delta\Delta\text{QTcF}_i = \text{Mean } \Delta\text{QTcF}_i \text{ for the active group} - \text{Mean } \Delta\text{QTcF}_i \text{ for the placebo group}$ , based on the ANOVA model, where  $i =$  at  $i$ th timepoint and  $\Delta\text{QTcF}_{ti} = \text{QTcF}_{ti} \text{ on Day } 1 - \text{QTcF}_{ti} \text{ at Baseline (i.e., Day - 1)}$ , where  $ti =$  at  $i$ th time point for subject  $t$

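### Study 2 cardiovascular SAP, Table 5.1.2: the one bound printed for RVOT acceleration time is the upper one, so it can show shortening, the harmful direction, but cannot limit its size

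*SAP*

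**What the plan says.** All references are to the Study 2 cardiovascular SAP (final version 1.0, 9 June 2020) unless another document is named.

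- **The bound.** Section 5 lists Table 5.1.2 as "Means, Mean Differences from Baseline by Visit and Upper Bound of One-Sided 95% CI from ANOVA for ECHO Data - RVOT". Tables 5.1.1 (PASP) and 5.1.3 (PVPR) also carry an upper bound. In the body of the SAP the one-sided bound is defined only for QTcF, in section 4.5.1: "The upper bound of the one-sided 95% CI (or, equivalently, two-sided 90% CI").
- **The direction of harm for RVOT.** Section 3.2.7 lists as an alert criterion "Right ventricular outflow tract flow acceleration time < 100 msec". Section 2.3.2.2 plans "Number of subjects with any RVOT measurement < 100 msec post-baseline" and also counts subjects who start at 100 msec or more and end the study below it. Tables 6.8 and 6.9 report these two counts.
- **The role of RVOT.** Section 2.3.2.2 places it among the secondary endpoints and says that it "will be used only as confirmatory variables for pulmonary hypertension".
- **The neighbouring variables.** PASP is harmful upwards: "Number of subjects with PASP>35 mmHg at anytime during therapy". For PVPR, the related alert criterion in section 3.2.7 is a high pulmonary regurgitation velocity.
- **Heart rate.** Tables 1.2.1 to 1.2.3 give the "Upper Bound of One-Sided 95% CI from ANOVA for ECG Data - Heart Rate", while section 2.3.1.2 counts "Increase or decrease from baseline > 20 bpm".

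**The concern.** A one-sided bound in a safety table is there to say how large an unwanted effect could still be. For that purpose it has to lie on the harmful side. The upper side is right for QTcF and was evidently carried over to the echocardiographic tables. It fits PASP and PVPR. It does not fit RVOT acceleration time, the one variable of the three whose harm the SAP defines downwards.

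At stake is how far Table 5.1.2 can reassure. Section 4.1 names valvular heart disease and pulmonary arterial hypertension as the primary outcome of the cardiac assessment, and RVOT is there to support the second. An upper bound at or above 0 says only that shortening was not demonstrated at the one-sided 5% level. It puts no limit on how much shortening is compatible with the data.

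**Working it through.** **1. The plan's own equivalence.** Section 4.5.1 equates a one-sided 95% bound with a limit of a two-sided 90% CI. The normal quantile is 1.645 for one-sided 0.05 and 1.645 for two-sided 0.10, so the statement is exact. Printing both limits of the two-sided 90% CI therefore gives both one-sided 95% bounds.

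**2. What each bound can say.** Let d be the active-minus-placebo difference in mean change, and h the half-width.

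- Planned: U = d + h, interval (−∞, U]. It limits lengthening. If U < 0 it shows shortening. It never limits shortening.
- Missing: L = d − h, interval [L, +∞). It limits shortening to at most −L when L < 0.

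**3. Size of the half-width.** The inputs are:

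- 40 per arm, the planned figure in section 2.5 of the main Study 2 SAP. The cardiovascular SAP (section 2.4.3) has no sample size calculation of its own.
- A three-group ANOVA with treatment as the only effect, so df = 120 − 3 = 117 and t(0.95) = 1.658.
- An SD of the RVOT change of 10 to 30 msec. This is an assumption; the documents give no value.

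The formula is h = t × SD × √(2/40).

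| Assumed SD (msec) | h (msec) | Lower bound if d = 0 (msec) |
|---|---|---|
| 10 | 3.7 | −3.7 |
| 20 | 7.4 | −7.4 |
| 30 | 11.1 | −11.1 |

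Example with SD 20 and d = −10 msec: U = −10 + 7.4 = −2.6, so the planned interval is (−∞, −2.6]. Shortening is shown, but its size has no limit. L = −10 − 7.4 = −17.4, which excludes shortening beyond 17.4 msec.

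**4. How often each bound excludes a given shortening when there is none.** Take a shortening of 0.5 SD, chosen for illustration since the SAP states no margin, with no true effect and 40 per arm. L excludes it when L > −0.5 SD. The probability comes from the noncentral t distribution with noncentrality 0.5 / √(2/40) = 2.236. It is 0.716 with df 78 (two arms only) and 0.718 with df 117 (three arms), so about 72%. The planned bound excludes it in 0% of trials, because its interval is always open towards shortening.

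**5. What else in the plan bears on shortening.**

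- Tables 6.8 and 6.9 face the right way but count crossings of 100 msec. A mean shortening that leaves subjects above 100 msec does not appear in them.
- Section 4.1 plans a 95% CI in the descriptive summary of continuous variables. It is not stated to be for the difference from placebo.
- The interval is symmetric, so L = 2d − U; in the example, 2 × (−10) − (−2.6) = −17.4. This needs the placebo-adjusted d in print. The title of Table 5.1.2 names differences from baseline, whereas Table 1.5 names differences from placebo and baseline.

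**The case against.** The strongest reply is that little depends on this number. RVOT is secondary and only confirmatory. In section 3.2.7 its criterion applies only when the tricuspid regurgitation jet velocity cannot be measured. PASP has a correctly directed bound and its own threshold counts (Tables 6.6 and 6.7). No margin, formal test or cardiac sample size exists. Shortening below 100 msec is counted directly, means are plotted by visit (Figure 11), and raw values are listed (Listing 2.1). All of this stands, and it sets the weight of the point.

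A reader might infer that the plan as a whole cannot exclude any harmful shortening. The documents do not support that. It is true of the printed bound alone. The threshold counts, the descriptive CI and the symmetry of the ANOVA interval each give partial information on shortening.

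A reader might also infer that the upper bound makes the trial likely to miss a real shortening. That does not follow either. The upper bound is the limit that detects shortening, and its failure rate depends on sample size and effect size. Printing the other side would not change it. For the same reason the upper bound should not simply be replaced.

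Nor does the upper-bound format run through every continuous variable: Table 1.5 (QT interval) has no bound. For heart rate, decreases are already tabulated by category in Tables 2.2.1 to 2.2.3, so that part is a minor companion.

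**Conclusion.** The point holds in limited form. The only ANOVA bound planned for RVOT acceleration time lies on the opposite side from the harm that the SAP itself defines. It can show that shortening is present but cannot limit its size, and the other displays fill the gap only in part.

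Under the assumptions above (40 per arm, normally distributed changes, no true effect), the missing lower bound would exclude a 0.5 SD shortening in about 72% of trials and the planned one in none. In msec the missing limit lies 3.7 to 11.1 below the estimate for an assumed SD of 10 to 30. The practical impact is modest, since no decision rule rests on this bound. It is still worth correcting, because the reporting of a pulmonary hypertension variable should show the limit on the side of harm.

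**What to change.** In Table 5.1.2, replace the upper bound alone by both limits of the two-sided 90% CI for the placebo-adjusted change from baseline in RVOT acceleration time at each visit, and name the placebo comparison in the title. The lower limit then bounds shortening, and the upper limit still shows whether shortening is established. The same two-limit display may be used in Tables 1.2.1 to 1.2.3 for heart rate, where the SAP counts changes in both directions. QTcF, PASP and PVPR can stay as they are.

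The cost is a change of table title and column header and a line of program code. No new data, assessment or analysis model is needed.
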